6.4.2 Erythema assessment

The assessing physicians will receive a specific training on how to assess dermatologic toxicity before study start. In case of no concordance between the two treating physicians in assessing toxicity, a third physician will be asked to evaluate the patient, and the toxicity grade receiving more agreement will be considered. Erythema assessment will be performed at each visit.

6.4.3 Spettrophotometry examination and TEWL examination

Objective *in vivo* measurements of skin erythema and pigmentation based on reflectance spectrometry (RS) will be performed. Skin reflectance measurements will be acquired *in vivo* by a spectrophotometric imaging system (SkinColorCatch, by Delfin Technologies Ltd. – Finland). At the clinical site, the Medical Physics Unit has a long tradition with spectrophotometric analysis, having developed a tool for automated melanoma detection¹²⁻¹³ and for the description of the blood and melanin content of pigmented skin lesions¹⁴.

Measurements will be performed before RT start and then once a week at each visit before RT session and on clean skin. Instrumental RS measurements will be performed at three different fixed regions within the area treated with RT, in any case only on flat skin regions and in absence of hair or nevus. A control measurement will be done also in a specific contralateral area.

The trans-epidermal water loss (TEWL) exam will be done at the same time-points as for the spectrophotometry exam, before RT sessions. The exam will be conducted with VapoMeter instrument (by Delfin Technologies Ltd. – Finland).

Measurements will be performed before RT start and then once a week at each visit, before RT session and on clean skin. Instrumental TEWL measurements will be performed at five different fixed regions within the area treated with RT, in any case only on flat skin regions and in absence of hair or nevus. A control measurement will be done also in a specific contralateral area.

6.4.4 Skindex-16 questionnaire

The Skindex-16 scale is a self-administered questionnaire to comprehensively measure the complex effects of skin diseases on subject's quality of life. The Skindex-16 measure is considered appropriate for a study since it has been shown to be reliable and valid for general skin disease.

The Skindex-16 allows patient rating of emotional and functional burdens that the CTCAE does not take into account⁵. These adverse events cause patient's discomfort and impact negatively on quality of life⁶.

The Skindex-16 questionnaire will be completed by the subject at each visit.

6.4.5 Patient Global Satisfaction

Global satisfaction evaluation by the subject will be assessed through a 5-point Likert scale (very poor, poor, medium, good, very good) at the end of the radiotherapy sessions and two weeks after the last irradiation.

6.5 Monitoring plan

The study will be monitored on a regular basis by the CRO's adequately qualified and trained clinical Monitors throughout the study period to ensure the proper conduct of the clinical investigation.

The purposes of study monitoring are to verify that the rights and well-being of study subjects are protected, that the reported study data are accurate, complete and verifiable against the source documents, and that the study is conducted in accordance with the current clinical investigation plan, Good Clinical Practice guideline (UNI EN ISO 14155) and applicable regulatory requirements.

During the monitoring visits, Monitors will verify the following including but not limited to: subject informed consent, subject's eligibility, safety data and reporting, quality of source documents and CRF data against subject's medical records. If inconsistencies are identified, the corresponding corrections to the CRF data will have to be made by the Investigator or designated person. Monitors will also check subject compliance, accrual, study product handling, including dispensing procedures and accountability logs, delegation of responsibilities within the Investigator's team, relevant communications with family doctors, if any, ancillary equipment and facilities, including refrigerators and freezers, local labs, etc. The Investigator and other site staff involved in the study must allocate enough time to the Monitor at these visits.

Upon request by the Sponsor, on-site study audits may be conducted in order to ensure the study is in compliance with GCP, applicable regulatory requirements, and the clinical investigation plan. The auditing activities may also be conducted after study completion.

The Investigator agrees to allow Sponsor/auditors/CRO monitors to have direct access to his/her study records for review, being understood that they are bound by professional secrecy, and as such will not disclose any personal identity or personal medical information.

Regulatory Authorities may wish to conduct on-site inspections (during the study or after its completion). If a Regulatory Authority notifies the Investigator of an inspection or visits the site unannounced for purposes of conducting an inspection, the Investigator must inform the Sponsor and CRO immediately. The Investigator will make all efforts to facilitate the conduct of the audits and inspections giving access to all necessary facilities, data and documents.

Any result or information arising from the inspection will be immediately communicated by the Investigator to the Sponsor. The Investigator will take all appropriate measures required by the Sponsor to implement corrective actions for all problems found during audits or inspections.

7. Statistical considerations

This section summarizes the statistical principles and methods planned to analyze the data for this clinical investigation.

7.1 Sample Size Determination

In a previous observational study¹¹, 38.2% of the patients treated with SOC preemptive treatment according to MASCC guidelines did not reach G2 radiation dermatitis at week 5. In a pilot study using Xonrid® (*Iacovelli et al. 2016, submitted*), the proportion of patients treated with Xonrid® and SOC

preemptive treatment according to MASCC guidelines that did not reach G2 radiation dermatitis at week 5 was 82.9%.

According to these previous results, a two group chi-square test with a 0.05 two-sided significance level will have 80% power to detect the difference between a proportion of patients that do not reach G2 of 38.2% in the Group B (standard of care (SOC) preemptive treatment according to MASCC guidelines) and a proportion of 82.9% in the Group A (Xonrid® and SOC preemptive treatment according to MASCC guidelines) when the sample size in each group is 18. To take into account a possible 10% dropout rate, 20 patients will be enrolled in each treatment group.

As two cancer sites will be investigated, to assess the treatment effect within each site, 80 patients will be enrolled: 40 patients with breast cancer and 40 patients with head and neck cancer.

7.2 Definition of Study Populations for Analysis

The study will be analyzed using an Intent-to-Treat (ITT) approach. All randomized patients receiving at least a treatment dose and having at least one post-randomization efficacy evaluation will be included in the ITT population for efficacy analysis. All randomized patients receiving at least a treatment dose will be included in the safety analysis.

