6.2.2 Standard of Care (SOC)

The SOC preemptive treatment will be according to MASCC guidelines and it includes:

1. washing with lukewarm water and a mild pH-neutral or non-alkaline soap. Shaving with a sharp, disinfected wet razor or with non-traumatizing electric razor
2. during or after radiation treatment, avoiding the use of metallic-based topical products (zinc oxide, creams or deodorants with an aluminum base, for instance), because they may increase the surface dose to skin
3. wearing loose-fitting clothes in order to prevent friction injuries over the irradiated area
4. avoiding extreme temperatures
5. avoiding the use of tapes and adhesives.

All the subjects enrolled in this clinical investigation will be recommended to comply with SOC guidelines above listed. SOC will be followed every day, continuatively, since the beginning of the radiotherapy until 2 weeks after the last RT session.

In the treatment group with SOC alone, when G2 skin toxicity develops, an adjunctive standard treatment will be introduced, at discretion of the Investigator.

Should G3 skin toxicity develop, then, in any case, the study will be interrupted and the subject will be treated according to the Investigator's opinion.

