6.4 Procedures

6.4.1 Study visits and assessments

Visit 1 screening (days from -3 to 0):

Subjects will be pre-selected on the basis of their medical history and the need of radiotherapy as curative or postoperative treatment for head & neck or breast cancer. Subjects will be evaluated with regard to the inclusion and exclusion criteria that will allow their participation into the study.

Before any study specific evaluation is carried out, subjects will receive all the information about the study by the Investigators and will sign an informed consent form.

The following assessments will be performed:

- Collection of information about demography
- Medical and surgical history
- Physical examination
- Concomitant medications and therapies
- ECOG performance status
- Erythema assessment
- Skindex-16 questionnaire
- Inclusion/exclusion criteria assessment

Visit 2 – randomization (Day1):

At visit 2 the subject eligibility will be re-assessed. Eligible patients will be randomized 1:1 in the two groups, treated respectively with Xonrid® + SOC or SOC alone.

The radiotherapy will start at this visit.

The following activities will be done at visit 2, before the first RT session:

- Inclusion/exclusion criteria assessment
- Randomization
- Physical examination
- Concomitant medications and therapies
- Erythema assessment
- Skindex-16 questionnaire
- Spettrophotometry examination and TEWL examination
- Treatment dispensation and instructions (the first application will be after RT session)
- Patient's diary dispensation and instructions on how to fill it in every day
- Adverse events recording

Visit 3 to 8/9 – RT and treatment:

Subjects will receive radiotherapy treatment every day for 6 or 7 consecutive weeks, with suspension only in the weekends. Breast cancer subjects are expected to attend 30 radiotherapy sessions (that means 6 weeks) while head & neck cancer subjects are expected to attend 33-35 radiotherapy sessions (that means about 7 weeks). One weekly visit for the study will be performed according to the subject availability (a ± 2 days window will be allowed and any delay will be recovered in the following visits).

The following activities will be done at visits:

- Physical examination
- Concomitant medications and therapies
- Erythema assessment
- Skindex-16 questionnaire
- Spettrophotometry examination and TEWL examination. Both exams will be done with clean skin, before the RT session

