### 8.3 Safety Population

All randomized patients receiving at least a treatment dose will be included in the safety population.

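### Entry to the ITT and safety sets requires a treatment dose, which is undefined for the advice-only Group B, so the ITT set is a modified ITT with an asymmetric or undefined condition

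*Protocol*

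**What the plan says.** Protocol 7.2 sets two entry conditions for the main efficacy set: "All randomized patients receiving at least a treatment dose and having at least one post-randomization efficacy evaluation will be included in the ITT population". The protocol synopsis and SAP 8.1 and 11.1 give the same rule. For safety the dose is the only condition; SAP 8.3 reads "All randomized patients receiving at least a treatment dose will be included in the safety population". SAP 8.2 plans no per-protocol set, and the summary in SAP 11.5 runs every efficacy endpoint on the ITT set.

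The comparator is a list of measures on washing, shaving, clothing, temperature and adhesives. Protocol 6.2.2 says of it: "All the subjects enrolled in this clinical investigation will be recommended to comply with SOC guidelines above listed". Group B receives an added treatment only once G2 has developed. Protocol 7.3.5.2 and SAP 11.3 measure exposure by diary-recorded product applications and by the weight of product used.

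Allocation is open label. At visit 2 (protocol 6.4.1), "Eligible patients will be randomized 1:1 in the two groups" before the first radiotherapy session. The gel is dispensed at that visit and first applied after the session. Protocol 6.1 and SAP 4.2 also say that both groups begin treatment on the first radiotherapy day.

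Two further rules bear on the point. SAP 10.2 removes patients with critical protocol deviations from the analysis. Protocol 7.3.1 and SAP 9.1.4 replace no missing values unless otherwise specified.

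**The concern.** A set called ITT should not depend on what a patient does after an open-label allocation. Here one entry condition depends on exactly that, and it has a checkable meaning only for the gel. Take two patients who both attend every weekly visit and have graded skin. One is allocated to Group A and never applies the gel; the other is allocated to Group B and ignores the hygiene advice. The first can be dropped for lack of a dose. The second has no dose to lack and stays.

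If Group A never-users have worse skin outcomes than other Group A patients, dropping them raises the Group A proportion and leaves Group B unchanged. For safety, the stated rule does not determine the Group B denominator at all. With no per-protocol or other efficacy set planned, nothing in the SAP would show the effect of the exclusion.

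**Working it through.** **1. The plan's own sample size.** Inputs from protocol 7.1: 38.2% without G2 at week 5 in Group B, 82.9% in Group A, two-sided alpha 0.05, power 80%, chi-square test.

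n per arm = [1.960·√(2·p̄·(1−p̄)) + 0.842·√(pA(1−pA) + pB(1−pB))]² / (pA−pB)², with p̄ = (0.829+0.382)/2 = 0.6055.

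This gives 17.5, so 18 per arm. Allowing for 10% dropout gives 20. Both stated figures reproduce. SAP 9.1 analyses each cancer site separately, so the relevant size is 20 per arm.

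**2. Effect of single exclusions.** Pearson chi-square without continuity correction. Each removed patient is a Group A never-user with G2.

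| Group A | Group B | p |
|---|---|---|
| 14/20 (70.0%) | 8/20 | 0.057 |
| 14/19 (73.7%) | 8/20 | 0.034 |
| 13/20 (65.0%) | 8/20 | 0.113 |
| 13/18 (72.2%) | 8/20 | 0.046 |

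One exclusion moves a proportion by at most 5 points (19/20 to 19/19).

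**3. Expected effect at the planned rates.** The documents give no count of never-users. I assume m = 1 to 4 of 20 in Group A, with proportion pU free of G2, and 82.9% among those who use the gel. Keeping everyone gives a Group A rate of [(20−m)·0.829 + m·pU]/20. Dropping never-users therefore raises the difference by m·(0.829−pU)/20.

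| Assumed pU | m=1 | m=2 | m=3 | m=4 |
|---|---|---|---|---|
| 0.382 (as SOC) | +2.2 | +4.5 | +6.7 | +8.9 |
| 0 (all reach G2) | +4.1 | +8.3 | +12.4 | +16.6 |
| 1 (none reaches G2) | −0.9 | −1.7 | −2.6 | −3.4 |

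Figures are percentage points. In the first row, dropping never-users keeps the difference at 44.7 points, with power 0.842 to 0.803. Keeping them gives 42.5 to 35.8 points, with power 0.805 to 0.634. That gap is partly a change of question, from the effect of allocation to the effect among users. The next step isolates bias.

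**4. No true effect.** Both arms are at 38.2%, and every Group A never-user reaches G2. Dropping them shifts the difference by 0.382·m/(20−m): +2.0, +4.2, +6.7 and +9.6 points for m = 1 to 4. Exact binomial enumeration of the chi-square test gives a two-sided type I error of about 0.055, 0.053, 0.073 and 0.082, against 0.050 with no exclusion. If never-users have the same prognosis as the rest, the shift is zero.

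**The case against.** A reader might infer that only Group A can fail the dose condition, and so that patients are removed from one arm only. The documents do not establish that. They call the SOC measures a preemptive treatment and have both groups start on the first radiotherapy day (protocol 6.1, SAP 4.2). If a dose means that start, a patient in either arm who is randomised but never begins radiotherapy fails it. The evaluation condition and the SAP 10.2 deviation exclusion can also remove patients from either arm.

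Nor is it plausible that all of Group B is meant to fall outside the safety set until G2. Protocol 7.3.6 and SAP 12.2 compare adverse events by arm, which presupposes a Group B denominator.

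The affected patient is likely to be rare. Eligibility requires willingness to comply; randomisation, first session and first application fall on the same day; and a single application over the eight to nine weeks keeps a patient in. Partial users and early stoppers all remain.

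The examples in step 2 are chosen near the threshold. Closer to the planned rates nothing changes: 16/20 v 8/20 is already p=0.010, and 17/20 v 8/20 is p=0.003. If one Group A patient with G2 is removed, the chance of crossing into significance in favour of Group A is about 6% at the planned rates and about 1.2% with 38.2% in both arms.

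All of this stands and limits the size of the problem. It does not supply a definition of a dose for Group B, and it gives no reason for an ITT set to depend on gel use.

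**Conclusion.** The point holds in a limited form. The dose condition is either asymmetric, if it is read as gel use, or undefined, because neither document settles on the day-1 reading. The efficacy set is a modified ITT under an ITT label, and the safety set lacks a stated entry rule for Group B.

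The expected effect is probably small. For 1 to 4 assumed never-users of 20 with SOC-like outcomes, the Group A advantage is 2.2 to 8.9 points larger than in an all-randomised analysis. In the adverse null case of step 4, type I error reaches about 0.08 at four. A borderline result at one cancer site can turn on one or two patients.

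A reader might also infer that the rule necessarily favours Xonrid. That is the likely direction, because people who never use a preventive product may well fare worse than those who do. It is not proven: if every never-user stayed below G2, the rule would lower the difference by 0.9 to 3.4 points. The count of never-users and their outcomes are assumptions throughout.

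**What to change.** - **Efficacy set** (protocol 7.2 and synopsis; SAP 8.1 and 11.1): delete the dose condition and define the primary set as all randomised patients, analysed in their allocated arm. Do not apply the SAP 10.2 critical-deviation exclusion to this set.
- **Missing week-5 grade:** state how it is counted, identically in both arms. Without this, removing the dose wording does not produce an all-randomised analysis, because missing values are not replaced. The rule should cover patients withdrawn for G3 before week 5, whose earlier grade is known.
- **Safety set** (protocol 7.2, 7.3.6 and synopsis; SAP 8.1, 8.3 and 11.1, with the restatement in 5.3): define it by an event both arms share, namely the first radiotherapy session after randomisation, and group patients by whether any Xonrid was applied.
- **Supplementary:** keep any gel-exposed efficacy analysis, labelled as such, and report how many Group A patients never applied the gel.

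The cost is revised wording plus one new rule for missing grades. No extra data collection is needed to identify who was randomised or who applied the gel, and the planned 18 (20 enrolled) per arm per site stands. The SAP describes enrolment as complete, so the change should be made before database lock and recorded in SAP section 13. The downside is that the Xonrid estimate may be slightly less favourable, with some loss of power, if some Group A patients never used the gel.

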7.3 Statistical Analysis

Descriptive statistics of all relevant variables will be performed. Continuous variables will be summarized by the number of patients (N), mean, standard deviation, median, minimum, maximum. Where appropriate, 95% confidence intervals for the target variables will be estimated. Categorical variables will be summarized by the number (N) and the proportion of patients (%).

The significance level of statistical tests will be set at 0.05. Details of statistical analysis are provided in the following paragraphs.

The statistical analysis will be performed using SAS 9.4 for Windows (SAS Institute Inc., Cary, NC, USA).

7.3.1 Missing Data

Missing values will not be replaced unless specified otherwise. Missing safety data will not be replaced.

7.3.2 Multiplicity

No correction for multiplicity is needed, as the study has only a primary endpoint and the secondary endpoints have exploratory purposes. In case of clinically and statistically significant results, the exact p-value will be reported to support the strength of the findings.

7.3.3 Covariates, Interactions and Subgroups

Due to the limited number of patients to be enrolled, covariates and subgroup analyses, if any, will be performed only with exploratory purposes.

7.3.4 Analysis of Demographics and Baseline Variables

Demographic (gender, age) and baseline characteristics will be summarized using mean, median, standard deviation, minimum and maximum for continuous variables and frequencies and percentages for categorical variables. To compare demographic and baseline characteristics between treatment groups, chi-square or t-tests will be used for discrete and continuous variable, respectively.

7.3.5 Efficacy analysis

7.3.5.1 Primary endpoint

The primary objective of this clinical investigation is to evaluate the proportion of patients without G2 radiation dermatitis (radiation dermatitis < G2) at week 5. The proportion of subjects will be compared between treatment groups using chi-square test. Logistic regression will be used to obtain Odds Ratio (OR), with 95% Confidence Interval (95% CI), and to eventually adjust for covariates.

7.3.5.2 Secondary endpoints

The median time to G2 radiation dermatitis development will be analyzed using Kaplan-Meier method. Comparisons between treatment groups will be performed using log-rank test.

The proportion of patients without G2 radiation dermatitis at week 6 for both cancer sites, at week 7 for head & neck cancer and 2 weeks after the last radiation for both cancer sites will be assessed and compared between treatment groups using chi-square test. Logistic regression will be used to obtain ORs, with 95% CIs, and to eventually adjust for covariates.

The worst skin toxicity during treatment and until 2 weeks after the last radiation will be compared between treatment groups using ANOVA.

The changes in skin erythema and pigmentation will be graphically described reporting the ITA (individual Typological Angle) degrees throughout the study. The ITA of the area treated with RT will be obtained averaging the ITA measured at the three different fixed regions, adjusted for the control measurement done in a specific contralateral area. Changes between visit 2, before the first RT session, and the end of RT and between the end of RT and the end of treatment will be analyzed and compared between treatment groups using ANCOVA, to adjust the estimates for baseline values.

The changes in trans-epidermal water loss (TEWL) will be graphically described reporting the Evaporation rate value (ERV, measured in g/m²h) throughout the study. The ERV of the area treated with RT will be obtained averaging the ERV measured at the five different fixed regions, adjusted for the control measurement done in a specific contralateral area. Changes between visit 2, before the first RT session, and the end of RT and between the end of RT and the end of treatment will be analyzed and compared between treatment groups using ANCOVA, to adjust the estimates for baseline values.

The mean and worst score of Skindex-16 questionnaire will be compared between treatment groups using ANCOVA, to adjust the estimates for baseline values.

Both the number of daily product applications reported on the patient's diary and the amount of used product, estimated through the difference in tubes weight between delivery to patient and return, will be used to assess the compliance to experimental treatment. The consistency between the two assessments will be checked through linear regression.

The patients' global satisfaction with treatment, assessed by Likert scale, will be compared between treatment groups using Kruskal-Wallis test.

